7.2.5. Immunogenicity

7.2.5.1. Anti-somatrogon Antibodies, Anti-rhGH Antibodies, and Neutralizing Antibodies (NAb)

Blood samples (approximately 4 mL of whole blood) will be collected for determination of ADA and NAb into appropriately labeled tubes at visits specified in the [Schedule of Activities](#).

Details regarding the collection, processing, storage and shipping of the serum immunogenicity samples will be provided in the Laboratory Manual. The samples must be processed and shipped as indicated to maintain sample integrity. Any deviations from the processing steps (eg, sample collection and processing steps, interim storage or shipping conditions), including any actions taken, must be documented and reported to the sponsor. On a case by case basis, the sponsor may make a determination as to whether sample integrity has been compromised. Any deviation from the specified sample handling procedure that resulted in compromised sample integrity will be considered a protocol deviation.

Samples will be analyzed using validated analytical methods in accordance with Pfizer standard operating procedures. Samples determined to be positive for ADA may be further characterized for NAb.

As part of understanding the immunogenicity of the study drug, study-samples may be used for additional characterization of the immune response and/or evaluation of the bioanalytical methods. These data will be used for exploratory purposes and may be included in the clinical report.

7.3. Pharmacokinetics

7.3.1. Serum for Analysis of Somatrogon

During all study periods, blood samples (approximately 4 mL) to provide a minimum of 2 mL serum for pharmacokinetic (PK) analysis will be collected into appropriately labeled tubes containing no anticoagulant at times specified in the [Schedule of Activities](#) section of the protocol.

The actual times may change, but the number of samples will remain the same. All efforts will be made to obtain the PK samples at the same time as the sample to assess immunogenicity.

Samples will be analyzed using a validated analytical method in compliance with Pfizer standard operating procedures (SOPs).

The PK samples must be processed and shipped as indicated in the instructions provided to the investigator site to maintain sample integrity. Any deviations from the PK sample handling procedure (eg, sample collection and processing steps, interim storage or shipping conditions), including any actions taken, must be documented and reported to the sponsor. On a case-by-case basis, the sponsor may make a determination as to whether sample integrity has been compromised. Any deviation from the specified sample handling procedure resulting in compromised sample integrity will be considered a protocol deviation.

As part of understanding the PK of the investigational product, samples may be used for metabolite identification and/or evaluation of the bioanalytical method, as well as for other internal exploratory purposes. These data will not be included in the CSR.

7.4. Dyad Clinical Outcomes Assessment (DCOA) and Patient Global Impression Severity-Impact on Daily Activities (PGIS-IDA)

DCOA 1 and 2 and the PGIS-IDA question will be administered according to the [Schedule of Activities](#) and [Appendix 5](#). DCOA 1 and 2 and PGIS-IDA are completed by the Subject/Caregiver Dyad which includes the subject (child who is being treated) and their adult caregiver. The adult caregiver should be the primary adult overseeing the growth hormone treatment of the subject. In the event that the role of oversight of treatment is shared by more than one person, the selection of the adult caregiver in the Dyad is left to the discretion of the investigator. However, the adult member of the dyad must be familiar with and participate in the preparation and administration of the medication at least some of the time. It is important that the same Subject/Caregiver Dyad complete all questionnaires together and every effort should be made to ensure that the same adult caregiver completes DCOA 1 and 2, and PGIS-IDA with the subject throughout the study. Questions from the DYAD questionnaire will be included on the electronic patient reported outcome (ePRO) device for the Clinical Staff Site user to complete in order to capture information about the primary adult overseeing treatment and the adult caregiver completing the questionnaires at Visits 1, 4 and 7. Refer to Appendices [Appendix 2](#), [Appendix 3](#), [Appendix 4](#), [Appendix 5](#).

8. ADVERSE EVENT REPORTING

8.1. Requirements

The table below summarizes the requirements for recording safety events on the CRF and for reporting safety events on the Clinical Trial (CT) SAE Report Form to Pfizer Safety. These requirements are delineated for 3 types of events: (1) SAEs; (2) non-serious AEs; and (3) exposure to the investigational product under study during pregnancy or breastfeeding, and occupational exposure.

Safety Event	Recorded on the CRF	Reported on the CT SAE Report Form to Pfizer Safety Within 24 Hours of Awareness
SAE	All	All
Non-serious AE	All	None
Exposure to the investigational product under study during pregnancy or breastfeeding, and occupational exposure	All (regardless of whether associated with an AE), except occupational exposure	Exposure during pregnancy, exposure via breastfeeding, occupational exposure (regardless of whether associated with an AE)

All observed or volunteered events regardless of treatment group or suspected causal relationship to the investigational product(s) will be reported as described in the following paragraphs.

Events listed in the table above that require reporting to Pfizer Safety on the CT SAE Report Form within 24 hours of awareness of the event by the investigator **are to be reported regardless of whether the event is determined by the investigator to be related to an investigational product under study**. In particular, if the SAE is fatal or life-threatening, notification to Pfizer Safety must be made immediately, irrespective of the extent of available event information. This time frame also applies to additional new (follow-up) information on previously forwarded reports. In the rare situation that the investigator does not become immediately aware of the occurrence of an event, the investigator must report the event within 24 hours after learning of it and document the time of his/her first awareness of the event.

For each event, the investigator must pursue and obtain adequate information both to determine the outcome and to assess whether it meets the criteria for classification as an SAE (see the [Serious Adverse Events](#) section below). In addition, the investigator may be requested by Pfizer Safety to obtain specific follow-up information in an expedited fashion. This information is more detailed than that recorded on the CRF. In general, this will include a description of the event in sufficient detail to allow for a complete medical assessment of the case and independent determination of possible causality. Any information relevant to the event, such as concomitant medications and illnesses, must be provided. In the case of a

subject death, a summary of available autopsy findings must be submitted as soon as possible to Pfizer Safety. Any pertinent additional information must be reported on the CT SAE Report Form; additional source documents (eg, medical records, CRF, laboratory data) are to be sent to Pfizer Safety **ONLY** upon request.

As part of ongoing safety reviews conducted by the sponsor, any non-serious AE that is determined by the sponsor to be serious will be reported by the sponsor as an SAE. To assist in the determination of case seriousness, further information may be requested from the investigator to provide clarity and understanding of the event in the context of the clinical study.

8.1.1. Additional Details on Recording Adverse Events on the CRF

All events detailed in the table above will be recorded on the AE page(s) of the CRF. It should be noted that the CT SAE Report Form for reporting of SAE information is not the same as the AE page of the CRF. When the same data are collected, the forms must be completed in a consistent manner. AEs should be recorded using concise medical terminology and the same AE term should be used on both the CRF and the CT SAE Report Form for reporting of SAE information.

8.1.2. Eliciting Adverse Event Information

The investigator is to record on the CRF all directly observed AEs and all AEs spontaneously reported by the study subject. In addition, each study subject will be questioned about the occurrence of AEs in a non-leading manner.

8.1.3. Withdrawal From the Study Due to Adverse Events (see also the [Subject Withdrawal/Early Termination](#) section)

Withdrawal due to AEs should be distinguished from withdrawal due to other causes, according to the definition of AE noted below, and recorded on the CRF.

When a subject withdraws from the study because of an SAE, the SAE must be recorded on the CRF and reported, as appropriate, on the CT SAE Report Form, in accordance with the [Requirements](#) section above.

8.1.4. Time Period for Collecting AE/SAE Information

The time period for actively eliciting and collecting AEs and SAEs (“active collection period”) for each subject begins from the time the subject provides informed consent, which is obtained before the subject’s participation in the study (ie, before undergoing any study-related procedure and/or receiving investigational product), through and including a minimum of 28 calendar days after the last administration of the investigational product.

For subjects who are screen failures, the active collection period ends when screen failure status is determined.

8.1.4.1. Reporting SAEs to Pfizer Safety

All SAEs occurring in a subject during the active collection period are reported to Pfizer Safety on the CT SAE Report Form.

SAEs occurring in a subject after the active collection period has ended are reported to Pfizer Safety if the investigator becomes aware of them; at a minimum, all SAEs that the investigator believes have at least a reasonable possibility of being related to investigational product must be reported to Pfizer Safety.

Follow up by the investigator continues throughout and after the active collection period and until the event or its sequelae resolve or stabilize at a level acceptable to the investigator, and Pfizer concurs with that assessment.

8.1.4.2. Recording Non-serious AEs and SAEs on the CRF

During the active collection period, both non-serious AEs and SAEs are recorded on the CRF.

Follow-up by the investigator may be required until the event or its sequelae resolve or stabilize at a level acceptable to the investigator, and Pfizer concurs with that assessment.

8.1.5. Causality Assessment

The investigator's assessment of causality must be provided for all AEs (serious and non-serious); the investigator must record the causal relationship on the CRF, and report such an assessment in accordance with the SAE reporting requirements, if applicable. An investigator's causality assessment is the determination of whether there exists a reasonable possibility that the investigational product caused or contributed to an AE; generally the facts (evidence) or arguments to suggest a causal relationship should be provided. If the investigator does not know whether or not the investigational product caused the event, then the event will be handled as "related to investigational product" for reporting purposes, as defined by the sponsor. If the investigator's causality assessment is "unknown but not related" to investigational product, this should be clearly documented on study records.

In addition, if the investigator determines that an SAE is associated with study procedures, the investigator must record this causal relationship in the source documents and CRF, and report such an assessment in the dedicated section of the CT SAE Report Form and in accordance with the SAE reporting requirements.

8.1.6. Sponsor's Reporting Requirements to Regulatory Authorities

AE reporting, including suspected unexpected serious adverse reactions, will be carried out in accordance with applicable local regulations.

8.2. Definitions

8.2.1. Adverse Events

An AE is any untoward medical occurrence in a study subject administered a product or medical device; the event need not necessarily have a causal relationship with the treatment or usage. Examples of AEs include, but are not limited to:

- Abnormal test findings;
- Clinically significant signs and symptoms;
- Changes in physical examination findings;
- Hypersensitivity;
- Progression/worsening of underlying disease;
- Drug abuse;
- Drug dependency.

Additionally, AEs may include signs and symptoms resulting from:

- Drug overdose;
- Drug withdrawal;
- Drug misuse;
- Drug interactions;
- Extravasation;
- Exposure during pregnancy (EDP);
- Exposure via breastfeeding;
- Medication error;
- Occupational exposure.

8.2.2. Abnormal Test Findings

Abnormal objective test findings should be recorded as AEs when any of the following conditions are met:

- Test result is associated with accompanying symptoms; and/or

- Test result requires additional diagnostic testing or medical/surgical intervention; and/or
- Test result leads to a change in study dosing (outside of any protocol-specified dose adjustments) or discontinuation from the study, significant additional concomitant drug treatment, or other therapy; and/or
- Test result is considered to be an AE by the investigator or sponsor.

Merely repeating an abnormal test, in the absence of any of the above conditions, does not constitute an AE. Any abnormal test result that is determined to be an error does not require recording as an AE.

8.2.2.1. Injection Site Reactions

Injection site reactions can be reported/recorded in four different ways.

- Injection pain, bruising, and stinging will each be scored by subjects by way of the Injection Sign and Symptom Assessment as part of the DCOA1. This assessment will be completed by subjects once for each treatment (once after completion of Period I and once after completion of Period II). Scores ≥ 8 for any sign or symptom (pain, bruising, bleeding, or stinging) will be recorded as an AE.
- Subjects will record injection site reactions in the subject diary.
- Subjects will be assessed for injection site reactions by the investigator at Visits 1, 2, 3, 4, 5, 6, and 7.
- Subjects will be instructed to call with any concerns regarding an injection site reaction.

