1.5. Benefits and Risks of Participation

The benefit of participation for all subjects in this study is close monitoring of the safety of the treatment and of their medical condition. The experience to date is that somatrogon has an efficacy and safety profile similar to that of Genotropin®. There is, however, limited experience in switching patients from treatment with Genotropin® to somatrogon. A potential risk of participation for all subjects is the occurrence of injection site reactions.

Additional information for this compound may be found in the single reference safety document (SRSD), which, for this study, is the Sponsor provided IB. The SRSD for the comparator agent is the local product documents (LPD).

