5.2. Subject Compliance

Subjects will be directed to bring any completely used pens and/or cartridges to each clinic visit. Subjects will be directed to bring all used and unused pens and/or cartridges to Visits 4 and 7. Lost containers, damaged unused pen devices, etc, should not be counted as completed dose administrations. Subjects who fail to dose between visits should be counseled about the importance of maintaining the dosing schedule. In the event of an adverse event or reaction, subjects may be counseled to interrupt dosing temporarily or permanently. Subjects will be provided a diary and instructed on how to complete it. The diary will be used to assess compliance and injection site reactions. Compliance is defined as $\geq 80\%$ adherence to injections. Compliance will be determined by review of the subject diary. Subjects who are non-compliant at 2 consecutive visits may be withdrawn.

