5.4. Administration

Site personnel will be trained on how to instruct subjects on the proper administration of the investigational product. Subjects will be provided the instructions on how to properly administer the investigational product using the appropriate injection device based upon treatment assignment. At Visit 1 and Visit 4 subjects will be observed for proper injection technique by site personnel while self-injecting using the appropriate injection pen device (Genotropin Pen[®] device with corresponding cartridge, Genotropin GoQuick[®], or somatrogon prefilled pen) that they will be using during Period I and Period II. Study staff and subjects should refer to the appropriate IFU for specific instructions on the handling and administration of the study drugs.

Subjects shall administer the appropriate study drug in the clinic on Visit Day 1 after all required procedures and assessments are complete and the subject is randomized to one of the following two treatment sequences:

- Sequence 1: Treatment with once daily Genotropin[®] for 12 weeks and then switched to once weekly somatrogon for 12 weeks;
- Sequence 2: Treatment with once weekly somatrogon for 12 weeks and then switched to once daily Genotropin[®] for 12 weeks.

Prior to randomization, subjects should be assessed for their ability and willingness to receive self-administered injections. If, however, following randomization, the subject is unable to physically use the product, the subject will be discontinued from the study and their attempts will be recorded as part of the study data.

The initial dose of Genotropin[®] or somatrogon for Period II will be administered in the clinic at Visit 4 by the subject after all required procedures and assessments are complete.

Genotropin[®] and somatrogon will be administered according to the IFU and the Subject Study Medication Dosing and Instruction Booklet, which will be provided to all subjects.

Training of subjects on Genotropin[®] administration will be in line with the training provided to patients for the licensed product. Clinical site personnel will review the IFU with the subject as well as provide guidance and assistance to ensure the subject is able to perform a self-injection. This first injection by the subject will be considered part of the training.

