5.4.2. Missed Doses

Subjects on somatrogon should administer their dose once weekly at approximately the same time on a regularly scheduled day of the week. If a subject on somatrogon misses a dose, they should administer that dose as soon as they remember, provided it is no more than 72 hours after their regularly scheduled dose. If the dose is more than 72 hours from their regularly scheduled day of the week, then the patient shall skip the dose for that week and resume dosing on their next regularly scheduled day of the following week. Note: Doses that are administered within 72 hours of their regularly scheduled day of the week will not be considered a missed dose.

Subjects on Genotropin[®] should administer their dose once daily at approximately the same time every day as they were at the time of screening. If a subject on Genotropin[®] misses a dose, they should administer that dose as soon as they remember, provided it is within 10 hours of their regularly scheduled dose. If more than 10 hours have passed the subject should resume administration of the study medication at the next scheduled time. Subjects should not double any doses to make up for a missed dose.

Subjects will be trained that if an injection is started (ie, the injection device is placed on the skin with the needle inserted into the skin and the button is depressed) no further attempts at injection should be made for that scheduled dose even if there is uncertainty that the full dose was received.

Subjects will record dose administration in the subject diary; this is how compliance will be determined.

A question involving missed doses and reason for missing is part of DCOA1 but is not being used to determine compliance.

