5.5. Switching between Genotropin[®] and Somatrogon

- Subjects that will be switching from Genotropin[®] to somatrogon in Sequence 1 should administer their final injection of Genotropin[®] 36 hours (± 24 hours) prior to their first injection with somatrogon; their somatrogon dose will be based on their weight (rounded to the nearest tenth) taken at baseline/Visit 1.
- Subjects that will be switching from somatrogon to Genotropin[®] in Sequence 2 should administer their final injection of somatrogon 7 days (± 72 hours) prior to their first injection with Genotropin[®].
- Subjects in Sequence 1 that have completed the study should restart their regularly prescribed supply of Genotropin[®], Humatrope[®], (USA only) or Omnitrope[®] (USA only) 7 days after their final somatrogon injection. Their Genotropin[®], Humatrope[®] (USA only), or Omnitrope[®] (USA only) dose should be the same dose that they were receiving at the end of Period I unless directed otherwise by their provider.
- Subjects in Sequence 2 that have completed the study should restart their regularly prescribed supply of Genotropin[®], Humatrope[®], (USA only) or Omnitrope[®] (USA only) 24 hours after their last study dose of Genotropin[®] was received. Their Genotropin[®], Humatrope[®], (USA only) or Omnitrope[®] (USA only) dose should be the same dose that they were receiving at the end of the study unless directed otherwise by their provider.

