### 6.6.1. Adverse Events

Adverse events will be summarized according to CaPS.

The number (%) of subjects who experienced TEAEs will be reviewed and summarized by relatedness to the study drug and severity grade. Descriptive statistics (number and frequency) will be provided for all adverse event summaries. No hypothesis testing will be carried out.

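### The SAP plans no summary of injection-site reactions and no per-injection rate, although a period holds about 84 daily or 12 weekly injections

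*Protocol*

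**What the plan says.** Protocol 1.5 names one potential risk of taking part: "A potential risk of participation for all subjects is the occurrence of injection site reactions". The safety objective is to describe the safety and tolerability of somatrogon.

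Protocol 8.2.2.1 gives four routes by which a reaction can be captured: the DCOA 1 sign and symptom scores, the diary ("Subjects will record injection site reactions in the subject diary"), investigator assessment at Visits 1 to 7, and calls from the family. On the diary, Protocol 5.2 says "The diary will be used to assess compliance and injection site reactions", and Protocol 5.4.2 says "Subjects will record dose administration in the subject diary; this is how compliance will be determined". Protocol 9.4 then lists injection site reactions at Visits 1 to 7 as a safety-analysis item of its own, next to adverse events.

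SAP 6.6 has no summary of diary or investigator-assessed reactions. SAP 6.6.1 states: "The number (%) of subjects who experienced TEAEs will be reviewed and summarized by relatedness to the study drug and severity grade". It adds "Descriptive statistics (number and frequency) will be provided for all adverse event summaries" without saying whether the unit is subjects or events, and refers to the sponsor's CaPS standard. By default (SAP 5) percentages are taken over subjects. SAP 3.5.1 counts an event as treatment-emergent at first occurrence or when it worsens.

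**The concern.** The two treatments differ about sevenfold in the number of injections per period. The percentage of children with at least one reaction rises with the number of injections even when each injection is equally reactive. Read alone, it cannot separate a product that irritates less from a schedule that simply has fewer injections.

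Both questions are legitimate. The subject percentage answers the one about the schedule. Nothing named in the SAP answers the one about the product, although the safety objective concerns that product and local reactions are the one risk the protocol names. The DCOA 1 scores do not fill the gap: they rate intensity once per period and say nothing about how often an injection causes a reaction.

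**Working it through.** The documents state no injection counts and no reaction rates, so there is no figure of the plan to reproduce. The sample-size calculation does not enter.

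**Injections per period.** Protocol 5.4 gives "Treatment with once daily Genotropin[®] for 12 weeks and then switched to once weekly somatrogon for 12 weeks" for Sequence 1, and the reverse order for Sequence 2.

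- Daily: 12 × 7 = 84. Weekly: 12. Ratio 84/12 = 7.0.
- Before the switch to somatrogon, children "administer their final injection of Genotropin[®] 36 hours" (± 24 hours) ahead, which removes up to about two daily doses; the +4 day window at Visit 4 can add some. With 82 to 87 daily doses the ratio is 82/12 = 6.8 to 87/12 = 7.25.

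**Equal risk per injection.** Assume that every reaction is counted, that injections are independent, and that the risk p is the same in every child. The proportion of children with at least one reaction over n injections is 1 − (1 − p)^n. Subject percentages are equal when the weekly risk is 1 − (1 − p)^7. The values of p are illustrative.

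| Risk p per injection | Daily, n = 84 | Weekly, n = 12 | Weekly risk that equalises | Ratio to p |
|---|---|---|---|---|
| 0.5% | 34% | 6% | 3.4% | 6.9 |
| 1% | 57% | 11% | 6.8% | 6.8 |
| 2% | 82% | 22% | 13.2% | 6.6 |

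With 5% per weekly injection against 1% per daily injection, weekly shows 1 − 0.95^12 = 46% against 57%, so a fivefold higher risk per injection would still look better.

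**Equal subject percentage.** Solve p = 1 − (1 − P)^(1/n) for the same P in both treatments.

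- P = 10%: 0.87% weekly against 0.125% daily, ratio 6.97.
- P = 50%: 5.61% against 0.82%, ratio 6.83.
- P = 90%: 17.5% against 2.7%, ratio 6.46.

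**Clustering within children.** Reactions probably concentrate in some children. Use a beta-binomial model with mean risk m and intra-subject correlation ICC: the chance of no reaction in n injections is B(a, b + n)/B(a, b), with a = mθ, b = (1 − m)θ and θ = 1/ICC − 1. The ICC values are assumed. With m = 1% in both treatments:

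| ICC | Daily | Weekly | Weekly-to-daily risk ratio that equalises |
|---|---|---|---|
| 0.02 | 39% | 10% | 4.5 |
| 0.1 | 19% | 8% | 2.7 |
| 0.3 | 9% | 5% | 1.9 |

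So about 7 is the independence case, and clustering brings it down to roughly 1.9 to 4.5.

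**What the SAP table would count.** The calculation assumes that every reaction enters the table. Protocol 8.2.2.1 makes a DCOA 1 score of 8 or more an adverse event, but does not say that each diary reaction becomes one. Under SAP 3.5.1 a reaction seen before treatment started counts only if it worsens. Every child enters after at least 3 months on daily growth hormone (Protocol 4.1), and adverse events are collected from consent (Protocol 8.1.4). Local reactions already familiar on daily injections may therefore drop out of the Genotropin count.

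**The case against.** A reader might go further and infer three things that the documents do not support.

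- *That reactions are recorded per injection.* The protocol says that reactions and doses both go in the diary. It does not say that a reaction is tied to a dose, and the diary form is not among the documents. The injection denominator is collected; how finely reactions are recorded is unknown.
- *That the subject percentage is the only count planned.* SAP 6.6.1 also promises number and frequency, and defers to CaPS; SAP 6.6 leaves events of special interest to a Safety Narrative Plan. Neither source is visible, so event counts cannot be ruled out. No injection denominator is named in any case.
- *That the table will flatter somatrogon several-fold.* The treatment-emergent rule and the unstated link from diary to adverse event leave the net direction in that table open.

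The strongest defence is that the trial compares schedules, that safety is descriptive with no hypothesis test, and that the share of children with a reaction over 12 weeks is a valid per-patient measure; fewer injections are part of a weekly product. That stands, and is why the subject percentage should stay. Investigator assessments are also scheduled equally in both periods, the DCOA 1 intensity scores are compared by mixed model, and all collected data are listed. These soften the gap without closing it: the SAP names no summary of the investigator assessments, the scores are not frequencies, and Protocol 9.4 calls for safety data to be tabulated as well as listed.

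**Conclusion.** The point holds as a gap in the safety summaries. Protocol 9.4 makes injection-site reactions an analysis item; the SAP plans no summary of the diary or investigator-assessed reactions and names no per-injection or exposure-adjusted rate. With about 84 against 12 injections, a subject percentage cannot be read as a statement about the product. If every reaction were counted, equal percentages would be compatible with up to about a 7-fold higher risk per somatrogon injection under independence, and about 1.9- to 4.5-fold with ICC 0.3 to 0.02. All risks and ICCs here are assumptions. The size and direction of any distortion in the treatment-emergent table itself cannot be settled from the documents. The primary analysis and sample size are unaffected.

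**What to change.** In SAP 6.6, next to number (%) of subjects, add one descriptive table of injection-site reactions by treatment. Give the number of reactions, the number of injections given, and reactions per 100 injections with a 95% CI that allows for clustering within subject. Take reactions and doses from the diary as far as its format allows. The rate needs only totals per child and period, not a reaction matched to each dose; if the diary cannot supply even those totals, say so. Add a sentence that the subject percentage describes the schedule and the per-injection rate describes the product.

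The cost is one extra table, with no new data collection if the diary entries permit it. The sponsor should expect that somatrogon may look less favourable per injection than per subject.
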